10.0 ENDPOINT DEFINITIONS

10.1 Primary Endpoints

The **primary endpoint** is the tumor Ki-67 proliferation index, measured pre- and post-treatment in each treatment arm.

10.2 Exploratory Endpoints

The **exploratory endpoints** are:

1. Measurements of histologic response, tumor growth, and apoptosis measured pre- and post-treatment in each treatment arm including:
 - o Response: gland cellularity, nuclear grade, nucleoli, metaplasia, eosinophilic cytoplasm, secretion
 - o Growth: Bcl-2
 - o Apoptosis: Casp3
2. Biological characteristics of tumors measured pre- and post-treatment in each treatment arm including:
 - o ER status
 - o PR status
 - o MMR status
 - o PI3K mutational status
3. Genomic analyses
 - o Germline and somatic genomic landscapes of endometrial tumor pre- and post-treatment in each arm
 - o Gene expression phenotypes before and after treatment:
 - driver mutations
 - mutation signatures
 - tumor mutation burden
 - immune signatures

11.0 STATISTICAL CONSIDERATIONS

11.1 Study Design

This is an open-label randomized Phase II study to compare the efficacy of neoadjuvant MA plus PTE versus MA alone among EC patients undergoing scheduled total hysterectomy. The primary measure of efficacy will be treatment-associated change in tumor Ki-67 proliferation index. The primary endpoint of the proposed trial was chosen based on data from GOG-211 [24], where a 34.8% reduction in Ki-67 was reported following two weeks of MPA treatment.

11.2 The planned sample size is 18 evaluable participants per treatment arm. With 18 evaluable subjects per arm and using a 1-sided t test at $p<0.05$, the trial will provide 90% power to detect a difference in efficacy, favoring MA plus PTE, of at least 10% (with standard deviation 10%) in the mean reduction in Ki67. For example, the trial will be able to differentiate between a 40% and a 30% mean reduction in Ki67 per arm. Thus, the trial will study $2 \times 18 = 36$ evaluable subjects. Little dropout is anticipated due to tolerability issues or inconvenient protocol. Randomized allocation will be 1:1, allocated within strata of diagnosis and menopausal status.

11.3 Definitions, Evaluable Participants and Participant Replacement

Evaluable for toxicity: All patients who receive at least one dose of protocol therapy will be evaluable for toxicity.

Evaluable for efficacy: Subjects who receive at least 10 days of study treatment and who provide pre- and post-treatment tissue samples will be evaluable for the efficacy endpoint, Ki67.

Non-evaluable subjects who receive at least 1 dose of study treatment will be included in the Toxicity analysis but will be replaced for the Efficacy (Ki67) analysis.

11.5 Statistical Analysis Plan

Patient demographics and clinical characteristics at baseline will be summarized using descriptive statistics.

All patients evaluable for toxicity will be included in the toxicity analysis. Observed toxicities will be summarized by type (organ affected or laboratory determination), severity, time of onset, duration, probable association with the study treatment, and reversibility or outcome.

The primary analysis of efficacy will compare treatment-associated change in Ki-67 proliferation index between the 2 study arms, using a 1-sided test with significance at $p<0.05$. Using a generalized estimating

equation to take into account the repeated assessment of subjects (pre and post treatment), analysis will use a generalized linear regression model of Ki-67 index. Adjustment for potential confounding factors will be made as appropriate.

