1.1 Primary Objective

- Determine the effect of MA plus PTE versus MA alone on tumor proliferation (Ki-67) during the preoperative window in patients with EC or endometrial complex atypical hyperplasia who are scheduled for hysterectomy. We will compare the treatment-associated change in tumor Ki-67 proliferation index between the two treatment arms (MA plus PTE versus MA alone) using endometrial tumor samples obtained before and after treatment.

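### The 90% power is shown for a t test, not for the GEE that is the primary analysis: scale and link are unstated, and baseline Ki-67 and the strata are not used for precision

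*Combined protocol and SAP*

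**What the plan says.** The sample-size paragraph, numbered 11.2 and placed under the Study Design heading, says that "the trial will provide 90% power to detect a difference in efficacy, favoring MA plus PTE, of at least 10% (with standard deviation 10" (percent) on a one-sided t test at 0.05 with 18 evaluable patients per arm. Its example is that "the trial will be able to differentiate between a 40% and a 30% mean reduction in Ki67 per arm". The supporting figure in 11.1 is that "a 34.8% reduction in Ki-67 was reported following two weeks of MPA treatment". None of these says whether the percentages are points on the Ki-67 index or percent of each patient's own baseline.

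Section 1.1 sets the comparison: "We will compare the treatment-associated change in tumor Ki-67 proliferation index between the two treatment arms". Section 10.1 gives the endpoint as "the tumor Ki-67 proliferation index, measured pre- and post-treatment in each treatment arm".

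Section 11.5 specifies a one-sided test at 0.05 from a GEE with the pre- and post-treatment values as repeated outcomes: "analysis will use a generalized linear regression model of Ki-67 index". It gives no link, working correlation, small-sample method or reference distribution. On covariates it says only that "Adjustment for potential confounding factors will be made as appropriate". In 11.2, "Randomized allocation will be 1:1, allocated within strata of diagnosis and menopausal status", but 11.5 does not carry those two factors into the model.

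**The concern.** The power statement and the primary analysis are two different procedures, and no section gives power for the second. Ki-67 is itself a percentage, so a 10% reduction can mean two things. If it means a fraction of baseline, a patient who starts high loses more index points than one who starts low for the same fractional effect. In an unadjusted comparison of point change, that baseline spread becomes noise.

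Two things are at stake. The first is whether the sponsor can rely on 90% for the test that will be reported. The second is efficiency: with 36 evaluable patients, the trial measures baseline Ki-67 and records both strata, but the model as written gains no precision from them. Leaving scale and link open in an open-label trial also leaves room to settle the primary model after data have been seen.

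**Working it through.** **Inputs.** From 11.2: 18 per arm, difference 10%, SD 10%, one-sided 0.05, example means 30% and 40%. The documents give no baseline mean, baseline spread or pre/post correlation. Assumed for illustration: lognormal baseline, mean 40, CV 0.1 to 0.6. A relative effect is a reduction of 0.30 v 0.40 with SD 0.10, independent of baseline. A points effect is a fall of 12 v 16 points with SD 4, the same standardised effect of 1.

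**Step 1: the plan's figure.** Noncentrality = (10/10) × √(18/2) = 3. With 34 df and one-sided 0.05, power is 0.902. The stated 90% reproduces.

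**Step 2: identity link, effect in points.** The arm-by-time term equals the difference in mean point change, so it targets the same quantity as the t test. An uncorrected robust variance divides by 18 instead of 17. A z test on it therefore rejects when T(34) exceeds 1.645 × √(17/18) = 1.599. That gives one-sided error 0.0596 and power 0.917. With the usual variance and a t reference, power returns to about 0.90.

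**Step 3: identity link, effect relative.** Point change is baseline × reduction. In units of the baseline mean, its variance in an arm with mean reduction r is 0.10² × (1 + CV²) + r² × CV².

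- CV 0.3: 0.0109 + 0.0081 = 0.0190 for r = 0.30, and 0.0109 + 0.0144 = 0.0253 for r = 0.40. The average is 0.02215 and its root 0.149. The standardised effect is 0.10/0.149 = 0.67, not 1.
- CV 0.6: 0.0136 + 0.0324 = 0.0460 and 0.0136 + 0.0576 = 0.0712. The average is 0.0586 and its root 0.242. The standardised effect is 0.41.

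A normal approximation, Φ(3 × effect − 1.645), gives about 0.64 and 0.34. Simulation of the robust z test gives 0.67 and 0.39. It is higher partly because that test is slightly liberal.

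**Step 4: GEE power by scale and link** (simulated; robust z; identity link in points by the closed form of step 2).

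| True effect | Link | CV 0.1 | 0.2 | 0.3 | 0.4 | 0.5 | 0.6 |
|---|---|---|---|---|---|---|---|
| Points | identity | 0.92 | 0.92 | 0.92 | 0.92 | 0.92 | 0.92 |
| Points | log | 0.89 | 0.80 | 0.68 | 0.56 | 0.46 | 0.38 |
| Relative | identity | 0.89 | 0.80 | 0.67 | 0.56 | 0.46 | 0.39 |
| Relative | log | 0.92 | 0.91 | 0.90 | 0.89 | 0.87 | 0.85 |

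If the post-treatment value is floored at zero, the first row is 0.89 to 0.92.

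**Step 5: do covariates in the GEE help?** A main effect is the same on a patient's pre and post rows, so it cancels from the within-patient change. In one simulated data set (CV 0.3, identity link) the arm-by-time estimate was −5.0295 with SE 2.1635. Both were unchanged to four decimals after adding the strata, or baseline plus strata. A baseline-by-time term does help. In another data set (CV 0.6, relative effect) the SE was 3.446 without baseline, 3.446 with a baseline main effect, and 2.032 with baseline-by-time.

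**Step 6: linear model of change on arm, baseline Ki-67 and both strata, t reference.**

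| Outcome | True effect | Power, CV 0.1 to 0.6 |
|---|---|---|
| Point change | points | 0.89 (0.86 to 0.89 with the floor at zero) |
| Point change | relative | 0.89 falling to 0.81 |
| Percent reduction | relative | 0.89 |
| Percent reduction | points, floored at zero | 0.89 falling to 0.63 |

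Under a relative effect, the unadjusted t test of point change falls from 0.87 to 0.36 over the same range.

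These runs make change independent of baseline within the stated scale. If instead the SD of change is 10 points, pre and post variances are equal and their correlation is ρ, adjustment reduces the SD to 10 × √((1 + ρ)/2). That is 7.07, 8.66 and 9.75 at ρ = 0, 0.5 and 0.9, with power 0.994, 0.960 and 0.915 before the small loss of degrees of freedom to the strata.

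A literal fall of 30 v 40 points with SD 10 and an assumed baseline mean of 60 runs into the floor at zero. At CV 0.6 the adjusted model has about 0.75 and the unadjusted t test 0.72.

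**Step 7: strata.** Suppose each factor shifts change by 0.5 SD, with 4 of 18 and 6 of 18 patients per arm in the smaller levels (all assumed). A t test that ignores them has 4.0% error and 91.6% power. A model with both has 5.1% and 93.2%.

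**The case against.** The best defence is that 1.1, 10.1, 11.1 and 11.5 all speak of the Ki-67 index and its change. Read as index points with an identity link, the GEE contrast is the difference in mean change and the 90% stands. That is correct. What is missing is a commitment to that reading, and the 40% v 30% example and the 34.8% figure could equally suggest a relative reduction.

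A reader might infer that the trial is underpowered. The documents do not support that: the low figures need a particular pairing of scale and link plus a baseline spread that no section gives. A reader might also infer that leaving out baseline biases the result or that baseline is ignored. Neither follows. Allocation is randomised, and baseline Ki-67 is in the GEE as the pre-treatment outcome. The loss is of precision only.

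It is also fair that the adjustment clause in 11.5 is not limited to main effects, so a baseline-by-time term could be added within the existing GEE. Replacing the GEE is therefore not required. Likewise, the 6% error applies only if an uncorrected z test is used, which 11.5 does not say. Ignoring the strata is, if anything, conservative in the example of step 7.

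**Conclusion.** The point holds as a gap between the power statement and the primary analysis, with an improvement available from data already collected. The 90% is arithmetically right for the t test in 11.2, and right for the GEE under index points with an identity link. It is not established for 11.5 as written, because the scale and the link are both open. Mismatched scale and link would give about 0.67 at CV 0.3 and 0.38 to 0.39 at CV 0.6. Matched choices stay between 0.85 and 0.92.

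Baseline adjustment of point change removes most of that dependence (0.81 to 0.89 under a relative effect) at a cost of about one percentage point of power when change is unrelated to baseline. It does not remove the need to state the scale, because percent reduction analysed under a points effect can fall to about 0.63. Every figure that depends on a CV, a baseline mean or a stratum effect is an illustration from assumed values. This should be fixed, but it does not invalidate the design.

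**What to change.** 1. In 11.5, make the primary analysis a linear model of change in the Ki-67 index with terms for arm, baseline Ki-67, diagnosis and menopausal status, tested one-sided at 0.05 against a t reference. Alternatively, keep the GEE with an identity link and specify arm-by-time, baseline-by-time and strata-by-time terms, a small-sample corrected variance and a t reference.
2. In 11.2, state whether the 10% and SD 10% are index points or percent of baseline, and tie the power statement to the model in 11.5. If the scale is percent of baseline, model percent reduction with the same covariates and align the wording of 1.1 and 10.1.

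The cost is a text amendment with IRB review under 16.3, with no added patients or procedures. Stated power becomes about 89% when scale and model match and change is unrelated to baseline, and about 0.90 to 0.99 if change is related to baseline through regression to the mean. The residual risks are a wrongly stated scale and the floor at zero if falls as large as 30 to 40 points are expected; step 6 gives the size of each.

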12.0 DATA HANDLING, DATA MANAGEMENT, RECORD KEEPING

12.1 Source Documents

Source documents are original documents, data, and records (e.g., medical records, pharmacy dispensing records, recorded data from automated instruments, laboratory data) that are relevant to the clinical trial. The investigator or their designee will prepare and maintain adequate and accurate source documents. These documents are designed to record all observations and other pertinent data for each patient enrolled in this clinical trial. Source documents must be adequate to reconstruct all data transcribed onto the case report forms.

12.2 Data Capture Methods and Management

Data for this trial will be collected using City of Hope's electronic capture system that is compliant with 21 CFR Part 11. Study personnel will enter data from source documents corresponding to a subject's visit into the protocol-specific electronic Case Report Form (eCRF).

12.3 Case Report Forms/Data Submission Schedule

Study personnel will enter data from source documents corresponding to a subject's visit into the protocol-specific electronic Case Report Form (eCRF) when the information corresponding to that visit is available.

The investigator is responsible for all information collected on subjects enrolled in this study. All data collected during the course of this study must be reviewed and verified for completeness and accuracy by the investigator. All case report forms must be completed by designated study personnel. The completed case report forms must be reviewed, signed and dated by the Investigator or designee in a timely fashion.

All data will be collected using electronic data collection, stored as indicated in **Section 12.2**, and will be submitted according to the timelines indicated in **Table 2**.

Table 2: Data Submission Schedule

Form	Submission Timeline
Eligibility Checklist	Complete prior to registration
On Study Forms	Within 14 calendar days of registration.
Baseline Assessment Forms	Within 14 calendar days of registration.
Treatment Forms	Within 10 calendar days of treatment administration.
Adverse Event Report Forms	Window period: Within 7 calendar days of AE assessment/notification. Post-window period: Within 10 calendar days of AE assessment/notification.
Response Assessment Forms	Within 10 calendar days of the response assessment.
Other Assessment Forms (concomitant medications)	Within 10 calendar days of the assessment.
Off Treatment/Off Study Forms	Within 10 calendar days of end of treatment/study.
Follow up/Survival Forms	Within 14 calendar days of the follow up activity.

12.4 Regulatory Records

The investigator will maintain regulatory records, including updating records in accordance with Good Clinical Practice guidelines and FDA regulations.

13.0 ADVERSE EVENTS AND UNANTICIPATED PROBLEMS

13.1 Definitions

13.1.1 Adverse Event (AE)

An adverse event is any untoward medical experience or change of an existing condition that occurs during or after treatment, whether or not it is considered to be related to the protocol intervention.

13.1.2 Serious Adverse Event (SAE)

A serious adverse event is any expected or unexpected adverse events that result in any of the following outcomes:

- Death
- Is life-threatening experience (places the subject at immediate risk of death from the event as it occurred)
- Unplanned hospitalization (equal to or greater than 24 hours) or prolongation of existing hospitalization
- A persistent or significant disability/incapacity
- A congenital anomaly/birth defect
- Secondary malignancy*
- Any other adverse event that, based upon appropriate medical judgment, may jeopardize the subject's health and may require medical or surgical intervention to prevent one of the outcomes listed above (examples of such events include allergic bronchospasm requiring intensive treatment in the emergency room or at home, blood dyscrasias or convulsions that do not result in inpatient hospitalization, or the development of drug dependency or drug abuse).

*Modified from [21 CFR 312.32](#)

13.1.3 Unanticipated Problems Involving Risks to Subjects or Others

An unanticipated problem is any incident, experience, or outcome that meets all three of the following criteria:

1. Unexpected (in terms of nature, severity, or frequency) given the following: a) the research procedures described in the protocol-related documents such as the IRB approved research protocol, informed consent document or Investigator Brochure (IB); and b) the characteristics of the subject population being studied; **AND**
2. Related or possibly related to participation in the research (possibly related means there is a reasonable possibility that the incident, experience, or outcomes may have been caused by the drugs, devices or procedures involved in the research); **AND**
3. Suggests that the research places subjects or others at greater risk of harm (including physical, psychological, economic, or social harm) than previously known or recognized.

13.2 Assessment of Adverse Events

The site Investigator will be responsible for determining the event name, assessing the severity (i.e. grade), expectedness, and attribution of all adverse events.

13.2.1 Assessment of Adverse Event Name and Grade

Adverse events will be characterized using the descriptions and grading scales found in the most recent version of the National Cancer Institute's Common Terminology Criteria for Adverse Events (CTCAE). The determination of severity for all other events not listed in the CTCAE should be made by the investigator based on medical judgment and the severity categories of Grade 1 to 5 as defined below:

- Grade 1 (mild) – An event that is usually transient and may require only minimal treatment or therapeutic intervention. The event does not generally interfere with usual activities of daily living.
- Grade 2 (moderate) – An event that is usually alleviated with additional specific therapeutic intervention. The event interferes with usual activities of daily living, causing discomfort but poses no significant or permanent risk of harm to the subject.
- Grade 3 (severe) – An event that requires intensive therapeutic intervention. The event interrupts usual activities of daily living, or significantly affects the clinical status of the subject.
- Grade 4 (life threatening) – An event, and/or its immediate sequelae, that is associated with an imminent risk of death or with physical or mental disabilities that affect or limit the ability of the subject to perform activities of daily living (eating, ambulation, toileting, etc).
- Grade 5 (fatal) – Death (loss of life) as a result of an event.

13.2.2 Assessment of Attribution

The following definitions will be used to determine the causality (attribution) of the event to the study agent or study procedure.

- **Unrelated** – The event is clearly related to other factors such as the participant's clinical state, other therapeutic interventions, or concomitant medications administered to the participant.
- **Unlikely** – The event is doubtfully related to the investigational agent(s). The event was most likely related to other factors such as the participant's clinical state, other therapeutic interventions, or concomitant drugs.
- **Possible** – The event follows a reasonable temporal sequence from the time of drug administration, but could have been produced by other factors such as the participant's clinical state, other therapeutic interventions, or concomitant drugs.
- **Probable** – The event follows a reasonable temporal sequence from the time of drug administration, and follows a known response pattern to the study drug. The event cannot be reasonably explained by other factors such as the participant's clinical state, therapeutic interventions, or concomitant drugs.
- **Definite** – The event follows a reasonable temporal sequence from the time of drug administration, follows a known response pattern to the study drug, cannot be reasonably explained by other factors such as the participant's condition, therapeutic interventions, or

concomitant drugs, AND occurs immediately following study drug administration, improves upon stopping the drug, or reappears on re-exposure.

13.2.3 Assessment of Expectedness

The following definitions will be used to determine the expectedness of the event:

- **Unexpected** – An adverse event is unexpected if it is not listed in the investigator's brochure and/or package insert; is not listed at the specificity or severity that has been observed; is not consistent with the risk information described in the protocol and/or consent; is not an expected natural progression of any underlying disease, disorder, condition, or predisposed risk factor of the research participant experiencing the adverse event. *Modified from [21 CFR 312.32 \(a\)](#)
- **Expected** – An adverse event is expected if it does not meet the criteria for an unexpected event, OR is an expected natural progression of any underlying disease, disorder, condition, or predisposed risk factor of the research participant experiencing the adverse event.

13.3 Reporting of Adverse Events

13.3.1 Routine Reporting of Non-Serious Adverse Events

Routine AE recording will occur via data entry into the study eCRF. Recording of adverse events will begin once the patient is consented and will continue until the post-op follow up appointment. Adverse events will be monitored by the Protocol Management Team (PMT). Adverse events that do not meet the criteria of serious OR are not unanticipated problems do not require expedited reporting. AEs reported through expedited processes (i.e. reported to the IRB, DSMC, FDA, etc.) must also be reported in routine study data submissions.

13.3.2 Expediting Reporting Requirements of SAEs and UPS

Adverse events that meet the criteria of serious OR are unanticipated problems will be reported according to the approved [City of Hope's Institutional policy](#) via the AE/UP reporting form in [iRIS](#). Reportable serious adverse events must be followed until the event is resolved, stabilized, or determined to be irreversible by the investigator. Follow-up SAE reports must be submitted for all events that require expedited reporting when the status of the event changes and until the resolution or stabilization of the event.

